An extensive amount of preclinical and clinical data support the viability of islet transplantation as therapy for treating insulin-dependent diabetes. Islet transplantation has become an increasingly acceptable approach to reverse diabetes and has been largely tested in the context of autologous as well as allogeneic donor-recipient pairs [2, 7-9]. The outcomes of AIT in diabetes remission differ across patients that undergo TPAIT. Recent literature has shown at a median follow-up of 28-months post transplantation that about a third of patients was insulin independent, one third was fully insulin-dependent, and one third showed some islet graft function but still required exogenous insulin [1, 2]. In the latter case, even a partial graft function confers benefit to patient's health and quality-of-life.

A critical factor in predicting successful islet transplantation which translates into insulin-independence, is the islet equivalent (IEQ) count [1, 2]. Recent data from the largest TPIAT cohort reported a 3-year insulin independence rates that range from 12% in those receiving <2,500 IEQ/kg to 72% in those receiving >5,000 IEQ/kg of body weight [2]. Despite compelling evidence of the latter, about a third of patients receiving more than double IEQ/kg remain insulin dependent post-TPAIT. More interestingly, a recent report on a subject receiving as few as 954 IEQ/kg achieved and maintained insulin independence

up to 4 years after transplantation [10]. Therefore, additional factors besides the IEQ count, contribute to and limit islet survival and function post-AIT.

Islet cell survival and function, both short- and long-term are governed by the degree of cellular damage: both pre-existing from the underlying inflammation seen in chronic pancreatitis, and inflicted damage by the isolation and transplantation processes. Reports on beta cell mass among CP patients estimate 29% loss of the fractional beta cell area as a result of chronic inflammation and fibrosis, coupled with an additional 21% reduction in overall pancreatic mass resulting in more pronounced deficit in total islet mass [11]. As for inflicted damage, the islet isolation procedure is a key pre-transplant factor in islet mass loss [12, 13]. Harmful events also occur in the early post-AIT period and are induced by stressors such as hypoxia, hyperglycemia, and the infiltrating innate immune cell-derived cytokines and other pro-inflammatory factors [5, 14, 15]. A pro-coagulatory and pro-inflammatory cascade is activated within minutes after islet infusion back into the host and actively accelerate the injury to transplanted islets [16]. The levels of inflammatory cytokines such as IL-1Ra, IL-6, IL-8 and IL-10 have been reported to peak within the first 6 hours of islet infusion and gradually subside to pre-transplant levels days from islet transplantation [5, 16].

Stemming from experimental and clinical transplantation data, there is general agreement that providing anti-inflammatory cover during the early post-islet infusion period can protect the graft [15, 16]. Protection of the islet graft from the initial inflammatory challenge should prevent cell loss and preserve beta cell function leading to sustained long-term insulin independence and delay of complications associated with uncontrolled hyperglycemia [17, 18]. Recent studies have proposed the use of TNF- α blockers/inhibitors to short-circuit the innate inflammation known to be detrimental to beta cell function and survival [19-25]. Etanercept, a TNF-a blocker, has been incorporated into a number of immunosuppressive protocols for islet allotransplantation which have proven successful [19, 20, 23-26]. In the multicenter Clinical Islet Transplantation (CIT) study, the use of etanercept resulted in improvement in beta cell secretory capacity of more than 40% of normal and a three-fold gain in islet engraftment efficiency [20]. When these patients were evaluated at 1 year post-transplant, they remained free of insulin use with a trend towards further improvement in beta cell secretory capacity to more than 50% of normal [20]. Even though one cannot conclude that etanercept alone was an important factor in improving the outcomes, its inclusion in the immunosuppressive regimens is believed to have made some contribution that could be relevant in preserving beta cell mass and function consequent to TNF-alpha blockade. This same mechanism of islet loss is also relevant in the autologous islet transplantation settings.

Hydroxychloroquine (HCQ) is a quinolone anti-malarial agent, FDA-approved for the treatment of autoimmune diseases. HCQ is considered the first-line agent for the treatment of rheumatoid arthritis,

systemic lupus erythematosus and sjogren syndrome [27]. The immune effects of HCQ are modulated though several mechanisms, particularly through decrease in pro-inflammatory cytokine production such as IL-1 and IL-6 and reduction of proteolysis and antigen presentation. Compared to TNF-a blockers, HCQ is administered orally, is relatively inexpensive, and has excellent tolerability with minimal side effect profile.

Previous studies have demonstrated that patients treated with HCQ have a lower incidence of diabetes [28-32]. Hypoglycemia and/or reduction in HbA1c levels have been encountered in HCQ-treated patients, both in those with or without diabetes [33-37]. In three randomized, controlled trials conducted with type 2 DM patients, the use of HCQ resulted in reduced insulin need and improvement in HbA1c levels and beta cell function in all three trials [38-40]. A few mechanisms have been proposed regarding the effects of HCQ in improving glycemic profiles, most notably through the inhibition of inflammatory cytokines resulting in decreased beta cell loss as demonstrated in a rat model of pancreatic endocrine failure [41]. Another proposed mechanism is through improvement of insulin metabolism at the level of peripheral tissues [42].

We **hypothesize** that HCQ administration during the peri-transplant period will preserve islet mass and improve beta cell function in TPAIT by attenuating inflammation. The aim of our proposed study is to demonstrate a higher stimulated C-peptide level as well as better glucose control in response to a mixed meal tolerance test (MMTT) at 6 and 12 months following TPAIT in patients treated with HCQ compared to controls. A better response in the HCQ arm would suggest improved islet survival and metabolic performance, potentially facilitating higher rates of insulin independence.

We foresee that that the use of HCQ will help facilitate engraftment and preservation of the transplanted islet mass, both increasing the likelihood of graft survival initially and fostering long-term engraftment and improved outcomes in functional beta cell mass for patients who undergo TPAIT. If the study goals are achieved, and more controlled clinical studies confirm a potential positive outcome, anti-inflammatory treatments may become part of the standard protocol in patients undergoing TPAIT, and long-term complications of surgical diabetes may be attenuated. It is also anticipated that if the proposed treatment demonstrates improved metabolic function, higher rates and longer duration of insulin independence, this may encourage patients suffering from CP and qualifying for TP, to undergo surgery at a time in which a significant islet mass is still retrievable.

Data obtained from this pilot study will be used to inform a future phase I/II clinical trial to determine the optimum dosage and timing of this anti-inflammatory treatment to maximize improvement in beta cell function. In particular, the mechanisms of inflammation in the early phase after transplant may differ

from those associated with long-term islet loss, which we believe is an important variable to better understand.

2.1 Innovation:

2.1.1 Part I: Mitochondrial Function and Metabolic Outcomes in TPAIT

From a molecular standpoint, mitochondrial function of beta cells is directly related to the ability of beta cells to secret insulin [43]. Physiologically, as the insulin release is regulated by cytoplasmic adenosine triphosphate (ATP)/adenosine diphosphate (ADP) ratio, a mitochondrial defect will lead to defect in insulin release. Mitochondrial efficiency is important for the survival of transplanted islets due to increase in metabolic demand [44], and decrease in oxygenation [45].

In patients with chronic pancreatitis, as there are several factors influencing the islet health and function, such as inflammation, fibrosis, limited blood flow, compartment-like effect and loss of innervation [46], the mitochondrial function is probably compromised by this pathological microenvironment.

Extracellular flux analyzer is a method to assess mitochondrial respiration and glycolysis through the measurement of oxygen consumption rate (OCR) and extracellular acidification rate (ECAR), respectively. With a microchamber system, the analyzer allows the measurement of the change in the concentration of dissolved oxygen and the free protons. As the analyzer is equipped with drug introducers, a physiological stress can be imposed to the cells to test their respiration capacity in such situations. A method to assess the human islet with this analyzer has been validated and used in research [47].

In this pilot study, we are investigating the degree mitochondrial dysfunction in islets of patients with chronic pancreatitis receiving TPIAT, reflected by measured OCR and whether the latter is associated with poorer metabolic outcome compared with control, normal islets. This information will further contribute to the knowledge of autoislet function, and will identify other factors that are related to metabolic outcome that can be targeted for islet therapy in the future.

We **hypothesize** that mitochondrial dysfunction in islets of chronic pancreatitis patients is associated with a poor metabolic outcome after TP-IAT compared with control, normal islets. We also **hypothesize** that a trend towards less mitochondrial oxidative stress would be seen in patients receiving the anti-inflammatory drug HCQ prior to transplantation.

2.1.2 Part II: Genome-wide Gene Expression in TPAIT Patients

Previous investigations have identified pathways that regulate human beta-cell proliferation, function and maturation [48-51]. The genes regulating beta-cell proliferation and function may change dramatically with various factors, such as age [52]. Little is known about the gene signatures for islets from an inflammatory environment, particularly long-term CP patients, whose pancreata have been altered by the disease over time. The gene expression may influence the islet engraftment, survival, function and proliferation and impact the metabolic outcomes in islet transplantation.

We **hypothesize** that the gene expression signature plays a significant role in the clinical outcomes in TPAIT in patients with CP. Specifically, this study would help to determine:

- 1. Whether there is heterogeneity in the autoislet gene expression profiles prepared for TP-AIT
- 2. How the heterogeneity in the gene expression profiles is related to clinical outcomes of AIT

3. Study Design

3.1 Methods

This will be a pilot, 12-month phase II, open label, randomized, two-arm, single-blinded, placebocontrolled, parallel clinical trial of individuals undergoing TPAIT. The two study arms consist of HCQtreated and placebo-treated individuals. To take into consideration an expected more favorable outcome in beta cell function when higher IEQ/Kg body weight is infused, MMTT and C-peptide measurement prior to surgery will be used to assign potential subjects to either a predicted lower or higher IEQ/Kg group. This "distinguo" will be useful in the analysis of the results. Subjects from each group will be evenly distributed and randomized into the two treatment arms.

3.2 Sample

All patients undergoing TPIAT for CP in the Cleveland Clinic Foundation (CCF) will be under the auto islet registry (Institutional Review Board (IRB) number 08-340) and are potential candidates for the study.

A total of **10 patients** scheduled for TPAIT at CCF, who meet the inclusion/exclusion criteria for TPAIT, confirmed by a multidisciplinary team, consisting of a hepatobiliary surgeon, gastroenterologist, endocrinologist, diabetes educator, social worker, nutrition therapist, psychologist, and pain management team will be recruited into the study. The inclusion/exclusion criteria for entry into the trial, which consists of two parts (criteria for TPAIT and then criteria to be enrolled into this pilot trial), are summarized in Table 1. Historically, gender representation has been equal in the cohort of patients undergoing TPAIT at CCF [1]. Although a trend to better outcome in females was observed even though the mechanisms are unknown [1], the most significant predictor of metabolic function in patients

undergoing TPAIT is the islet mass infused, which will be factored into this trial in two ways: 1) by pretesting and assigning patients to predicted islet yield groups as has been described previously and 2) by normalizing parameters of metabolic function per IEQ/Kg infused.

Arm 1 (n=5) subjects will receive a pre-transplant 200 mg daily dose of HCQ 30 days before TPAIT and will continue on the drug for 3 months after surgery. This dosage will not exceed a daily dose of 5 mg/kg/day using actual body weight due to potential risk of retinal toxicity; patients weighing less than 40 kg will be excluded from study.

Arm 2 (n=5) subjects will receive placebo treatment following the same schedule as in Arm 1.

3.3 Feasibility of study

Since the program of TPAIT at CCF has become fully operational, approximately 10-13 patients undergo TPAIT within a 12-month period. It is anticipated that the requisite number of subjects proposed for the study will be enrolled within the time period allowed for the study.

3.4 Pace of enrollment

We anticipate that 12 months will be needed to recruit study subjects and 1-year for trial, totaling a study period of up to 24 months.

3.5 Benefits and risks

Hydroxychloroquine is considered to be among the safest antirheumatic medications with the potential for any serious adverse event being extremely rare [53]. Gastrointestinal symptoms are the most common side effects, nausea being the most common. The relative safety of HCQ has resulted in no regular laboratory testing required to monitor for toxicities. Monitoring for adverse events is clinical. Retinopathy is the most notable complication of HCQ, though any serious ophthalmologic toxicity is rarely seen with regular follow up. The risk of retinopathy increases with higher dosages and longer durations of therapy. In a study of 2,361 patients on HCQ for at least 5 years, the prevalence of retinal toxicity was less than 2 percent during the first 10 years of therapy in patients treated with 4.0 to 5.0 mg/kg of real body weight [54]. The current 2016 revised recommendations of the American Academy of Ophthalmology recommend that all patients undergo a baseline eye examination before or within a year of beginning the treatment with HCQ [55]. Given that that the likelihood of HCQ-induced retinopathy is rare with shortterm use (i.e. 4 months in this pilot study), no baseline ophthalmological evaluation will be mandated. However, patients with preexisting retinopathy will be disqualified from enrollment.

Table 1: Inclusion/Exclusion Criteria

Inclusion criteria for TPAIT [1, 56]	Exclusion criteria for TPAIT [1, 56]	
--------------------------------------	--------------------------------------	--

Inclusion criteria for HCQ phase	Exclusion criteria for HCQ phase		
Acceptance for TPAIT at CC Age range 18-65	Manufacturer's product label-contraindicated use of HCQ History of retinopathy Actual weight at enrollment <40 Kg Inclusion/exclusion criteria for TPAIT unmet		

4. Research Procedures

4.1 Total pancreatectomy and islet isolation and transplantation

Pylorus-preserving TP with duodenectomy will be performed in all cases usually associated with splenectomy to preserve perfusion to body and tail. Warm ischemia time will be minimized. Finally, the pancreas and duodenum will be removed intact and flushed/drained via the splenic artery and vein respectively with UW solution [56]. Islet isolation and purification will be performed as described [56-58]. The islet Isolation Laboratory located at the Institute of Cellular Therapeutics at Allegheny General Hospital (AGH) has performed more than 60 islet isolating procedures for the Cleveland Clinic and will perform all of the islet isolation for the study [58]. The number of islets will be quantified as islet equivalents (IEQ). The isolated islet through standard method will be transported back to the Cleveland Clinic and transplanted as previously described [56].

4.2 Randomization

Fasting blood glucose (FPG) level <100mg/dl with stimulated C-peptide >4 ng/ml during MMTT presurgery, will be the criteria to assign subjects to groups with predicted lower versus higher post-isolation islet yield. If either condition is not met, patients will be assigned to the lower yield group. With a representation from both groups, study subjects will be then randomized to HCQ treatment Arm 1 or placebo Arm 2 in a 1:1 allocation before the pancreatectomy procedure without any bias on age, gender, body weight, or IEQ isolated.

4.3 Blinding

The study will be single-blinded. The PI, biostatistician who will analyze the data, consultants, and technicians running assays will be blinded to the study arm into which the subjects have been randomized. An alphanumeric identifier that refers to the study subject without any indicators of study arm allocation will be used. Only the surgeons and the research coordinator, but not the personnel conducting the metabolic studies, will be un-blinded as to the study arm randomization.

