4.4 HCQ administration

Arm 1 (n=5): Subjects will receive a pre-transplant HCQ 200 mg daily dose 30 days prior TPAIT followed by HCQ use for an additional 3 months post-surgery. Oral medications are continued perioperatively. Patients are typically ordered for "NPO except for medications" starting from post-operative day 1 which will not preclude the administration of HCQ in the peri-transplant period.

Arm 2 (n=5) subjects will receive placebo treatment following the same schedule as in Arm 1.

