4.5 Exploratory mechanistic studies

All subjects will undergo a MMTT to assess islet cell function at 6 and 12 months following TPAIT (in addition to MMTT pre-surgery performed as standard of care, and whose results will be used for prerandomization in this pilot). Baseline metabolic tests obtained too early after surgery may not be indicative of islet function, due to insulin supporting therapy administered for several weeks after transplantation. Also, compelling data indicate that stabilization of islet function may require up to 1 year to occur. Blood glucose and C-peptide serum levels will be measured in peripheral blood samples immediately prior and subsequent to MMTT. Laboratory tests will be measured in CCF hospital laboratory.

The research coordinator will contact the subjects at 3, 6 and 12 months for interview on the course of follow up and will assist in scheduling the 6 and 12-month appointments for MMTT.

4.6 Innovation:

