[name] and her clinical staff will monitor the subjects for HCQ-emergent adverse events prior to discharge and the research coordinator will follow-up by phone contact throughout the duration of the trial.

Table 2: Study Timeline

	T= -1 months	T=0 (TPAIT day)	T = +3 months	T = +6 months	T = +12 months
HCQ group (n=5)	- MMTT #1 - Start of HCQ	- Seahorse XF analyzer for isolated islets ([name] Lab) - Genomic analysis ([name] Lab)	- Discontinue HCQ	- MMTT #2	- MMTT #3
Placebo group (n=5)	- MMTT #1 - Start of placebo	- Seahorse XF analyzer for isolated islets ([name] Lab) - Genomic analysis ([name] Lab)	- Discontinue placebo	- MMTT #2	- MMTT #3

Figure 1: Study Timeline

5. Data Analysis

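### The masking labels in section 3.1 contradict the placebo design, and section 4.3 un-blinds, without a stated reason, the coordinator who does the interviews and phone follow-up

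*Combined protocol and SAP*

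**What the plan says.** Section 3.1 describes the trial as "open label, randomized, two-arm, single-blinded, placebocontrolled".

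Section 4.3 repeats the single-blinded label. It lists the principal investigator, the analysing statistician, the consultants and the assay technicians as blinded, and then adds: "Only the surgeons and the research coordinator, but not the personnel conducting the metabolic studies, will be un-blinded as to the study arm randomization". Participants are on neither list. No reason is given for un-blinding the coordinator.

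Section 4.4 gives the control treatment: "Arm 2 (n=5) subjects will receive placebo treatment following the same schedule as in Arm 1". Table 4 budgets 600 active pills and 600 matching placebo.

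On follow-up, section 4.5 says "The research coordinator will contact the subjects at 3, 6 and 12 months for interview on the course of follow up". In section 4.7, the text just before Table 2 says that a named person and "her clinical staff will monitor the subjects for HCQ-emergent adverse events prior to discharge", and that the coordinator follows up by phone over the whole trial. Section 4.7 also describes a median 10-day hospital stay and then 5 to 7 days of daily outpatient visits, which are meant to catch events related to hydroxychloroquine.

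On safety, section 3.5 says "Monitoring for adverse events is clinical" and "Gastrointestinal symptoms are the most common side effects, nausea being the most common". It adds that the drug needs no routine laboratory testing for toxicity.

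**The concern.** There are two linked problems.

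The first is the description. A trial cannot be open label and also use a matching placebo to mask its participants. Someone who relies on section 3.1 could tell participants their arm; someone who relies on sections 4.3 and 4.4 would not. Any later report of the trial would inherit the same confusion.

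The second is who collects symptoms. Nausea and similar complaints are learned by asking. A person who knows the arm may ask differently, probe further or record more readily in one arm than in the other, and may also let the allocation slip to a masked participant. At stake is the comparison of tolerability between the arms, which matters because the background section says that the pilot is to inform a later trial on dosage and timing.

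**Working it through.** No figure in the plan has to be reproduced. The check sets the passages side by side and counts the un-blinded contact.

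**1. Are participants meant to be masked?**

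| Source | Points to |
|---|---|
| 3.1, open label | participants know their arm |
| 3.1 and 4.3, single-blinded | one party masked, not named |
| 4.3, only two roles un-blinded | everyone else masked, participants included |
| 4.4, placebo on the same schedule | participants masked |
| Table 4, matching placebo | participants masked |

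The quantities in Table 4 agree with the last two rows. 600 placebo units / 5 subjects = 120 each. The schedule is 30 days before surgery plus about 90 days after, which is 120 days (assuming one unit a day and 3 months as 90 days). Placebo is thus budgeted for the whole course. The dispensing line also agrees: $1,600 / $40 = 40 occasions = 10 subjects x 4 months, so both arms are supplied through the pharmacy.

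The better-supported reading is that participants are masked. On that reading participants, principal investigator, statistician, consultants, technicians and metabolic-study staff are all masked, and single-blinded is not an adequate label.

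**2. Who follows up symptoms, and when?**

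- Before discharge: clinical staff (4.7). The leader's name is removed, so whether these staff are blinded cannot be settled from the text.
- The 5 to 7 days after discharge: daily outpatient visits (4.7).
- After that: interviews at 3, 6 and 12 months (4.5) and phone contact (4.7), both by the un-blinded coordinator.
- Months 6 and 12: meal tolerance tests. Section 4.3 keeps the staff who run them blinded, but no passage gives them an adverse-event role.

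**3. How much un-blinded contact is there?**

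- Scheduled interviews: 10 x 3 = 30.
- At month 3, when study drug stops (Table 2): 10 x 1 = 10.
- At months 6 and 12, after it has stopped: 10 x 2 = 20.
- Phone calls: number not stated.
- Hospital stay plus outpatient visits: 10 + 5 = 15 to 10 + 7 = 17 days, using the median stay.
- Remaining time on drug after surgery: 90 - 17 = 73 to 90 - 15 = 75 days per subject.

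For those 73 to 75 days the coordinator is the only adverse-event follow-up contact that the available text describes. These counts show where knowledge of the arm could enter. They do not measure bias.

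**4. Which endpoints are exposed?** Sections 5.1 and 5.2 list C-peptide and glucose measures, oxygen consumption and acidification rates, and gene expression. None uses interview data, and section 4.3 blinds the people who run the assays and metabolic tests and analyse the data.

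**The case against.** The strongest reply is that little of importance is at risk. The endpoints are laboratory values handled by blinded staff. The word only in section 4.3 already masks participants by exclusion. The coordinator's task in section 4.5 is an interview and help with scheduling. No passage says that the coordinator grades or attributes events. Of the 30 interviews, 20 fall at least three months after study drug stops. The coordinator may need the allocation for reasons that the protocol leaves out, and the body of section 6, on adverse events and the monitoring committee, is not in the available text.

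Much of this stands. It limits the point to symptom-based follow-up and rules out several stronger readings that a reader might infer:

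- *The primary endpoint is biased.* The blinding in section 4.3 covers those who produce and analyse it.
- *Participants know their arm.* Only the open label wording says so, against three other indications.
- *Follow-up passes to an un-blinded person at discharge.* The 5 to 7 days of outpatient visits come first.
- *Un-blinding the surgeons does similar harm.* No passage gives surgeons, as such, the symptom follow-up.

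Two things remain. Masking by implication does not cure an explicit statement that the trial is open label. And asking about and recording symptoms is enough for ascertainment bias, even if someone else grades them. If the coordinator does need the code, section 4.3 should say why.

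**Conclusion.** The concern holds in a limited form. Section 3.1 contradicts the design that sections 4.3 and 4.4 and Table 4 describe, and the single-blinded label in 3.1 and 4.3 does not tell the reader who is masked. Followed as written, section 4.3 leaves later symptom follow-up to someone who knows the arm.

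The size of any bias cannot be derived from the documents. The exposure is 30 scheduled interviews, an unstated number of calls, and about 73 to 75 post-operative days on drug per subject. It concerns safety and tolerability data, not the laboratory endpoints.

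This rests on two assumptions: that the placebo was meant to mask participants, and that the unavailable body of section 6 does not give adverse-event follow-up to a blinded person. Such a passage would ease the second problem but would leave the conflict in section 3.1.

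**What to change.** - In section 3.1, delete open label.
- In sections 3.1 and 4.3, replace single-blinded with an explicit list of who is masked, naming participants.
- In section 4.3, move the research coordinator to the blinded list. State that the dispensing pharmacy holds the allocation code, with a documented route for emergency un-blinding.
- If the coordinator must stay un-blinded, state why, and have clinical staff who are already involved ask the adverse-event questions, provided that they are blinded.

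The cost is wording plus minor pharmacy paperwork. Table 4 already budgets the matching placebo, a pharmacy initiation fee and dispensing. It prices neither code custody nor the reassignment of calls, and its monthly storage fee is for drug, so it is no basis for an estimate. The practical downside is that every un-blinding request must go through the pharmacy.
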